## Mobile Intervention for Suicide Cognitions

training videotapes, and co-rating training with an experienced rater. Across previous studies, interrater reliability based on videotapes of participant interviews has been excellent (kappa = .96).

### **Subject Recruitment**

Participants will be recruited using a Data Access Request Tracker (DART) request to identify Veterans with PTSD diagnoses from Regional and/or Corporate Data Warehouse. Potential participants will be sent an introductory letter that describes the study and informs them that they will be called regarding participation. In the letter, potential participants will be given an “opt-out” number to call in order to decline participation and/or further contact regarding participation. Seven business days after the mailing, Veterans who have not called the toll-free number to decline participation will be contacted by a study team member to request their participation in the research study.

We will also recruit veterans from the Traumatic Stress and Health Laboratory’s “Contact Database,” IRB #1080; this database contains information about previous lab study participants who have agreed to be contacted about other studies for which they may qualify.

Clinicians in clinics throughout the medical center will be provided information about study eligibility and basic procedures (see brochure), and will be asked to refer potentially eligible veterans. Clinicians have reported that Veterans often indicate that they prefer that their names and contact information be provided directly to study staff. We’d like to make it easy for interested Veterans to get involved in research, while protecting the privacy of those Veterans who are not interested in research. Towards that end, we would like to allow a clinician to refer a participant directly to our clinic by adding the study PI or study coordinator as a co-signer to a note in CPRS in which the clinician has documented that the participant wishes to be contacted about participation.

Any Veteran who contacts or is contacted by the study team will be told that their participation is voluntary, and they may choose not to answer any questions that they find too sensitive. Also, Veterans will be told that their participation will not affect their care at the VA. The study team member will explain the study in detail, including compensation. No study procedures will begin until formal, written informed consent and HIPAA authorization have been obtained.

[figure not shown]
### **Study Interventions**

Two interventions will be studied in the current project, the MARI and the MIST interventions. The MARI intervention has already been developed by [name] (IRB # 2168). The MIST intervention is going to be developed in a similar manner. The interventions will be very similar except for the content of the treatment sessions. Below, we explain the layout of the MARI intervention and then the changes that will be made for the MIST intervention.

## MARI Intervention

*The IBM intervention.* The IBM treatment works as follows (see Figure 6). Participants are shown ambiguous, anger-relevant scenarios and instructed to imagine themselves in the described situation. For example, "You speak to someone and they do not respond." Next, another sentence appears that offers a benign, non-threatening interpretation of the scenario. For example, the sentence following this particular scenario reads, "This person is unaw\_re." The participants fill in the missing letter of the word, forming the word "unaware," and assigning the benign interpretation. This interpretation is then reinforced by requiring the participants to correctly answer "yes" or "no" to a comprehension question (i.e., "Did this person hear you?"). In this example, they must answer "no" to proceed. Across treatment sessions, unique scenarios are presented (i.e., participants do not see the same scenario twice). Scenarios have been developed to capture a wide range of different themes that are likely to be anger-provoking. Themes include: physical aggression, driving situations, irritating traits of others, thinking you are being ignored by others, feeling argued with or criticized, thinking someone is stealing from you, having people block you, thinking that others have hostile feelings, feeling disrespected, thinking that people will not help you, thinking that others do not appreciate you, and thinking that situations are unfair. See Figure 7 for an example of a training scenario in the MARI app.

[figure not shown]
**Figure 7. Example of a Training Scenario in MIRA App**

We will be delivering the intervention daily for 4 weeks. It will include 28 treatments sessions that will each take approximately 10 minutes to complete. Each session will include 42 training scenarios. No scenario will be

repeated across these sessions. To this end, 1,176 unique training scenarios have been developed. Scenarios have been reviewed by 9 PTSD experts in the field and

**Figure 6. IBM Intervention**

## Mobile Intervention for Suicide Cognitions

individuals with PTSD to confirm the content is relevant to this patient population. Additionally, the reading level has been assessed using an online readability calculator ("Readability Formulas") and all scenarios are at a 6th grade reading level or less. Qualtrics will time stamp use by the participants so that treatment time and completion for each participant can be calculated.

### *MIST Intervention*

The MIST intervention will be identical to the MARI intervention. The only difference is that the treatment sessions will include the scenarios that are being developed (see Design section) to target suicide cognitions. For example, "You make a mistake." Next, another sentence appears that offers a resolution to the scenario that is incompatible with the suicide cognition being targeted (in this example, unsolvability). The sentence following this particular scenario reads, "It can be fi\_ed." The participants fill in the missing letter of the word, forming the word "fixed," and resolving the scenario in a way to change the targeted suicidal cognition. This is then reinforced by requiring the participants to correctly answer "yes" or "no" to a comprehension question (i.e., "Are things permanently damaged?"). In this example, they must answer "no" to proceed.

### **Staff Readiness to Handle Potential Disruptive Behavior**

Principal investigators in the Traumatic Stress and Health Research Laboratory have been working with Veterans with PTSD since the mid-1990s, and much of their clinical and research work has involved providing anger interventions to these Veterans. Our laboratory currently has three other studies in which we provide anger interventions to Veterans with PTSD (IRB #s 1731, 2063, and 2168). Over the course of those studies, we have not had any need to report any disruptive behaviors or contact VA police. [name], recently completed a pilot study of the computer-based hostile interpretation bias intervention (IRB # 2136) and is currently conducting another study of the mobile hostile interpretation bias intervention (IRB # 2168). She has not had any Veterans express anger regarding the intervention.

Senior staff members are well trained in utilization of counseling techniques such as active listening, which helps to minimize the likelihood of angry outbursts. Study staff members are asked to attend levels 2 and 3 of the VA's Prevention and Management of Disruptive Behavior (PMDB) training, which is the VA's workplace violence prevention program. This level of training is the highest offered to VA employees in outpatient settings. Finally, office areas that are used for clinical interventions, interviews, etc. are equipped with panic alarms, and staff are trained in how/when to use the alarms.

### **Costs and/or Payments to Subjects**

The study involves up to three visits. Participants who are screened and found ineligible for the study will receive \$40 for their time. Eligible participants will receive \$100 for completing the first visit, \$50 for completing the post-MIST visit, \$25 for providing feedback on the 100 MIST scenarios, and \$50 for completing the post-MIRA visit. They will also be paid for completing the EMA monitoring for the 8-week duration of the study.

## Mobile Intervention for Suicide Cognitions

They will receive \$30 for each week that they do the EMA monitoring (8 weeks total) plus a \$20 compliance bonus each week that they complete at least 2/3rds of the prompted diaries. Participants can receive up to \$625 for completion of the study.

### **Data and Safety Monitoring**

The PI and study staff will be responsible for data safety and monitoring. There will be several ongoing mechanisms for monitoring and reporting of AEs: 1) ongoing participant contact via study personnel, 2) a toll-free number provided to participants to report concerns related to study participation; 3) weekly meetings between the PIs and study personnel. Study-related serious adverse events (SAEs) for participants in this project are not expected, but should they occur, they will be reported to the Durham VA Health Care System Institutional Review Board in accordance with local human protections program guidelines.

The PI will meet at least weekly with study personnel to discuss participants' reactions to the intervention, proper delivery of the intervention, and any adverse events or unanticipated problems. Monthly meetings between the investigators and the project manager will allow for ongoing progress reports, including the number of participants currently involved in the study, attrition rates, and scheduled data collection from participants, as well as notification and review of any AEs. Safety monitoring for AEs will be conducted in real time by the PI and/or project manager. The following information about adverse events will be collected: 1) the onset and resolution of the AE, 2) an assessment of the severity or intensity (use existing grading scales whenever possible), 3) an assessment of the relationship of the event to the study (definitely, probably, possibly or not related), and 4) action taken (e.g., none, referral to physician, start or increase concomitant medication). The PI will determine the severity of the event, will assign attribution to the event, and will monitor the event until its resolution. Any adverse events will be reported to the IRB in accordance with the local Human Research Protection Program's Standards of Practice. All research projects conducted at the Durham VAHCS are required to have yearly IRB review. Reports of non-serious AEs are required as part of these progress reports. Additionally, any changes to the project between review periods must be application by the IRB prior to fielding.

### **Withdrawal of Participants**

The PI may withdraw participants due to inability, or unwillingness, to complete study procedures or attend appointments.

### **COVID-19 Temporary Study Procedures**

The informed consent process will occur over the phone or via an approved telehealth platform. Potential participants will be mailed the consent and HIPAA authorization, and a study staff member will call them to discuss the consent and HIPAA. Participants will be asked to return the signed consents by mail/UPS.

Study visits will be completed via an approved telehealth platform, with phone as a back-up measure. If the study staff member has access to Audacity via CAG, he/she/they will record the interviews (think-aloud and post-treatment qualitative

## Mobile Intervention for Suicide Cognitions

interview) directly to the VA secured server (in lieu of videorecording with an external device). If telehealth visits are done using VA's instance of WebEx, audiorecordings will be done to the VA WebEx cloud and moved as soon as possible to the VA secured server. Questionnaires will be completed orally, by mail, and/or via MyHealthyVet.

We would like to ask participants to complete measures related to stress, trauma, and coping strategies during the pandemic. New participants will complete these measures at their first visit, and ongoing participants will complete them at their next study visit. We are adding the CAIR Pandemic Impact Questionnaire (Lang, 2020; [https://www.nlm.nih.gov/dr2/CAIR-PIQ\\_scoring.pdf](https://www.nlm.nih.gov/dr2/CAIR-PIQ_scoring.pdf)), and another measure, COVID Core Questions, with variables of interest. If a participant endorses any item marked with an asterisk on the COVID Core Questions measure, we will ask them to complete a PTSD Checklist 5 related to that specific event. Because these are temporary measures to be used only during the COVID-19 pandemic, we have not added them to the consent form. Instead, participants will be informed verbally re: the measures, and will be told that they can refuse to answer them.

**Safety Concerns.** Study therapists will be informed that prior to beginning interviews participants will need to identify an emergency contact for the participant to be used only in true emergencies (e.g., medical crisis, high risk suicidal ideation). If any participant expresses suicidal or homicidal ideation (SI and HI, respectively), study staff will respond using a standard of practice that has been used successfully in our lab's past telehealth-based trials. The study staff member responsible for the call will be instructed to gather more information from the participant, including information about plan, means, intent, intended victim (in the case of HI) and history of suicidal and homicidal behavior. Any participant who expressed SI will be provided with the suicide hotline number. The participant will be informed that the PI may contact him/her to talk more about his/her SI or HI. The study coordinator will obtain current contact information for the participant and inform the PI, who will contact the participant as necessary to ensure participant safety. In cases of imminent homicidality or suicidality, which are not anticipated, we will seek guidance from the Psychiatric Emergency Clinic on best strategies for follow-up, which could include, but is not limited to, self-presentation at the VA's emergency room with the help of an emergency contact, calling 911, or calling local police for a wellness check.

**Study Communication.** For any participant who indicates that they are willing to receive study communications via email, we will use Azure to send secure communications to them re: appointment scheduling, missed appointments, etc. Content from the study's IRB-approved letters will be included in the emails.

## Data Analysis and Statistical Considerations

Rapid turn-around analysis of the qualitative interviews will be conducted according to methods described by Hamilton. Participant impressions of the MIST app, feedback on the content of the scenarios, usability of the app, perceived strengths and weaknesses, and suggestions for improvement will be compiled and used to make modifications to the app content and design.

## Mobile Intervention for Suicide Cognitions

Recognizing that it is inappropriate to examine efficacy in a small pilot trial, we will focus on feasibility and acceptability objectives. As appropriate for this stage of treatment development and evaluation, analysis and interpretation will focus on describing the primary outcomes: acceptability of the intervention and feasibility of the trial approach. Additionally, although we will not be able to statistically analyze changes in suicide cognitions and hostile interpretation bias, we will describe the changes including whether they were observed in the expected directions.

Data will be analyzed using SAS. In the event that required SAS modules are not available at VINCI, deidentified data will be moved to Duke University Medical Center for analysis. Any data movement outside the protected VA environment will be accomplished using a VA-issued and owned FIPS-140-2 encrypted thumb drive loaned to a VA study staff member. Data will be stored at Duke on a protected server to which only [name] and her study staff have access; data are encrypted at rest.

Multilevel modeling (MLM) will be used to analyze the EMA data. MLM is a technique for analyzing repeated observations of data across multiple individuals. Unlike repeated-measures ANOVA, MLM can incorporate time-varying and time-invariant predictors to model between-person differences in within-person relationships. MLM can also accommodate imbalanced data and unequal variances. To examine the association between app use on suicide risk and functioning (Aim 2), three models will be analyzed in which each of the continuous outcome variables recorded during EMA will be modeled via MLM during each of the 4-week intervention periods as a function of frequency of app use.

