## Aims

**Aim 1(a). Develop a mobile interpretation bias modification intervention entitled Mobile Intervention for Suicidal Thoughts (MIST) to reduce cognitions that contribute to elevated suicide risk.** We will develop content to target cognitive factors that contribute to suicide risk and program this content into a mobile application similar to an existing app developed by the team to target hostile interpretation bias, entitled MIRA.

**Aim 1(b). Use a successive cohort design to refine the MIST intervention among Veterans with PTSD, problematic anger, and elevated suicidal ideation.** To refine the intervention developed in Aim 1(a), the app will be tested in two cohorts (each  $n = 5$ ) of Veterans with problematic anger, and suicidal ideation. After each cohort uses the MIST application for four weeks, a quantitative and qualitative evaluation will be conducted with each Veteran. Revisions will be conducted before the next cohort is treated. Then, a third cohort ( $n = 4$ ) will be recruited to test a web-based version of the MIST intervention delivered via Qualtrics.

**Aim 2. Assess the impact of reductions in suicide cognitions and hostile interpretation bias on suicide risk and functioning.** After using the MIST intervention for four weeks, participants will use the MARI intervention for another four weeks. For the duration of the study (all eight weeks of treatment), EMA data will be collected to evaluate the impact of both interventions on suicide risk and daily functioning.

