## Design

The proposed research project has two aims: 1) to develop and refine the MIST mobile intervention; and 2) to assess the impact of reductions in suicide cognitions and hostile interpretation bias on suicide risk and functioning among Veterans with problematic anger, and elevated suicidal ideation. The project has been designed in order to complete both aims simultaneously. The first step is to develop training scenarios for the MIST intervention. [name] has already started developing these scenarios to fit into specific themes of types of cognitions that have been theoretically and empirically linked to suicide: unbearability (*I can't tolerate being this upset*), unlovability (*I am unworthy of love*), unsolvability (*Nothing can solve my problems*), thwarted belongingness (*I do not belong*), perceived burdensomeness (*Others are better off without me*), and hopelessness about the future (*Things will not improve*). Unique scenarios will be developed for 28 treatment sessions (daily sessions for four weeks). When the scenarios have been developed, they will be reviewed by a team of experts (i.e., doctoral level psychologists with experience working with this Veteran population) who will rate them on how relevant they are for the Veteran population. They will also share comments and suggestions for refining these scenarios. Each scenario will be reviewed by at least one expert. Scenarios with low relevance will be revised before inclusion in the app. These are the same procedures used to develop the content for the MARI app.

In order to refine the MIST mobile intervention, a successive cohort design will be used. Successive cohort design utilizes an iterative process for by which psychosocial treatments in the early stages of development are systematically refined and modified. Qualitative and quantitative data collected by providing the treatment to these small

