## Mobile Intervention for Suicide Cognitions

brief questionnaire to assess their self-efficacy at managing suicidal thoughts and anger. On a 1-5 Likert scale they will be asked to rate: “how confident are you with your ability to cope with suicidal thoughts?” and “how confident are you with your ability to cope with anger?”. At the post-MIST and post-MIRA assessments, they will complete the Client Satisfaction Questionnaire.

EMA assessments will also be conducted for the duration of the time that participants are engaged in the MIST and MARI interventions (8 weeks). There will be one random alarm-prompted diary entry during the day and a nightly diary using established procedures from our team. The EMA diary will include assessments of: *suicidal ideation*; and *functioning and health related quality of life* using the brief IPF and items from the WHOQOL-BREF. EMA entries will also ask about affect and alcohol and substance use.

Demographics and Background Measures	Time (min)	Baseline	Post-MIST	Post-MIRA
Demographics	2	•		
Traumatic Life Events Questionnaire (TLEQ)	10	•		
Diagnostic Interviews				
Structured Clinical Interview for DSM-5	60	•		
Feasibility and Acceptability Measures				
Participant Recruitment	--	•		
Treatment Retention	--		•	•
Withdrawals	--	•	•	•
App Utilization	--		•	•
Client Satisfaction Questionnaire (CSQ)	5		•	•
Post-MIST Interview	30		•	
Clinical Measures				
Interpersonal Needs Questionnaire (INQ)	5	•	•	•
Suicide Cognitions Scale (SCS)	5	•	•	•
Beck Hopelessness Scale	5	•	•	•
Word Sentence Association Paradigm-Hostility (WSAP-H)	10	•	•	•
Columbia-Suicide Severity Rating Scale	5	•	•	•
Beck Scale for Suicide Ideation	5	•	•	•
Dimensions of Anger Reactions (DAR)	5	•	•	•
Brief Inventory of Psychosocial Functioning	5	•	•	•
WHOQOL-BREF	5	•	•	•
Patient Health Questionnaire-9 (PHQ-9)	5	•	•	•
PTSD Checklist for DSM-5 (PCL-5)	10	•	•	•

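### The EMA model has one undefined predictor, app-use frequency, and no study-day or within/between-person term, so its coefficient can reflect time trend or user differences, with a sign that depends on coding

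*Combined protocol and SAP*

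**What the plan says.** Data Analysis and Statistical Considerations introduces the EMA models: "To examine the association between app use on suicide risk and functioning (Aim 2), three models will be analyzed". Each continuous EMA outcome "will be modeled via MLM during each of the 4-week intervention periods as a function of frequency of app use". The same section says that "MLM can incorporate time-varying and time-invariant predictors to model between-person differences in within-person relationships". That describes what the method can do; it does not list terms to be fitted.

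Elsewhere in the protocol:

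- Measures: "There will be one random alarm-prompted diary entry during the day and a nightly diary". The diary covers suicidal ideation and "functioning and health related quality of life", plus affect and substance use.
- Measures, on timing: "EMA assessments will also be conducted for the duration of the time that participants are engaged in the MIST and MARI interventions".
- Design: "Unique scenarios will be developed for 28 treatment sessions (daily sessions for four weeks". MARI Intervention likewise describes 28 daily sessions, and says Qualtrics time-stamps use so that completion can be calculated. The assessment table lists app utilization without defining it.
- Aims: under Aim 2, "EMA data will be collected to evaluate the impact of both interventions on suicide risk and daily functioning". The Aim 2 heading names a different exposure, namely reductions in suicide cognitions and hostile interpretation bias.

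**The concern.** The exposure could be a daily yes/no, sessions per week, a running total or one total per person. Daily yes/no is the natural reading because sessions are daily, but the text does not settle it. Each coding responds differently to two ordinary features of such data: symptoms and use both drift over four weeks, and heavier users differ from lighter users. With no study-day term and no split of use into its two levels, either feature can enter the coefficient.

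A third route is that a bad day leads to a skipped session. Skipping then looks harmful and use looks helpful. Nothing in the plan says whether a session must come before the diary it is meant to explain.

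At stake is how the Aim 2 EMA result is read for a suicide-risk outcome. If the coding is chosen after the data are seen, that choice can decide the direction of the reported association.

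**Working it through.** **Figures in the plan.** Sample size: 5 + 5 + 4 = 14, matching Selection of Subjects. Diary prompts per four-week period: 14 × 28 × 2 = 784. The plan gives no alpha, power, effect size or SD for the EMA models.

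**Models compared.** As stated: outcome = intercept + person random intercept + b × use. With added terms: outcome = intercept + person random intercept + bW × (use − person's mean use) + bB × person's mean use + bT × study day.

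**Assumed inputs (none from the documents).** 14 people, 28 days, two diaries averaged per day; person SD 1, day SD 0.7, diary error SD 0.7; mean session probability falling from about 0.8 to 0.5; SD of use propensity 0.8 logit; higher score = worse; no effect of use; random-intercept REML; two-sided 5% test; 1,000 runs, so the Monte Carlo SE is at most √(0.5 × 0.5/1000) = 1.6 points.

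| Condition | Same-day use | Cumulative count | Total per person | Same-day + day | Cumulative + day | Within/between + day |
|---|---|---|---|---|---|---|
| No drift | 3.7% | 5.6% | 6.7% | 3.6% | 4.4% | 3.9% |
| Drift −0.5 | 9.3% | 90.8% | 7.3% | 5.2% | 5.4% | 5.0% |
| Drift −1.0 | 25.5% | 100% | 7.3% | 4.6% | 5.2% | 4.5% |
| Use and severity correlated −0.5 between people | 5.1% | 5.2% | 40.5% | 5.8% | 6.5% | 5.4% |
| Worse day lowers that day's use (log-odds −0.7 per unit) | 90.4% | 6.8% | 7.6% | 91.1% | 8.2% | 90.9% |

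**Hand check of the sign change (drift −0.5).** The simulated slopes were +0.062 for same-day use and −0.026 per cumulative session.

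- *Same-day use.* Bias ≈ drift × Cov(use, time)/Var(use), within person, with time scaled 0 to 1. Cov ≈ −0.3 × 1/12 = −0.025. Total variance is 0.65 × 0.35 = 0.23; the between-person part is about (0.8 × 0.23)² = 0.03, leaving 0.20. Bias ≈ −0.5 × (−0.025/0.20) = +0.06.
- *Cumulative count.* About 28 × 0.65 = 18.2 sessions accrue, so the slope ≈ −0.5/18.2 = −0.027.

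**Second simulation, other assumptions** (75% of diaries answered; use falling 90% to 67% / 95% to 55%; outcome falling 0.5 SD). False positives: daily yes/no 10% / 17%, sessions per week 33% / 58%, cumulative 92% / 93%, total per person 4% / 4%. With a fall of 0.25 SD: 7% / 10%, 13% / 19%, 38% / 38%, 5% / 5%. The pattern agrees; the sizes move with the inputs.

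**What the added terms do not fix.** In the last row of the table, same-day use stays near 91% with study day and the split included. Session–diary order needs its own handling.

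**Does a window before the diary settle the order?** Assume sessions uniform over 08:00–22:00 and independent across days, a daytime diary uniform over 10:00–18:00 and a nightly diary uniform over 20:30–22:00. Take a participant who misses no session, and a diary at clock time d.

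- *24-hour window.* Coded no session with probability (22 − d)(d − 8)/196 = (49 − (d − 15)²)/196. Daytime: (49 − 6.33)/196 = 22%. Nightly: (49 − 39.25)/196 = 5%.
- *Session earlier the same day.* Coded no with probability (22 − d)/14. Daytime: (22 − 14)/14 = 57%. Nightly: (22 − 21.25)/14 = 5%.

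Either window partly measures the hour at which the session is done, mostly at the daytime diary.

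**The case against.** The plan largely protects itself. It calls the target an association, says a small pilot should not examine efficacy, and makes feasibility and acceptability primary. No decision rests on the EMA models. The rejection rates use a significance test the plan never states and inputs it never gives. The figure above 90% under drift needs a cumulative count, which is not the natural coding; for daily use under drift the range is 7% to about 26%. All of this stands, and it limits the point to a low-cost improvement. It does not supply the missing definition or terms.

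Three stronger readings are tempting.

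- *The missing terms are why Aim 2 cannot claim impact.* They are not. One arm, a fixed MIST-then-MARI order, self-selected use and no untreated EMA period rule that out even with a full model.
- *The plan commits to a model without these terms.* It is silent on them.
- *Three models contradicts two intervention periods.* Three outcomes fitted separately in two periods make 3 × 2 = 6 fits, but one model per outcome with a period interaction gives exactly three.

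**Conclusion.** The point holds as a gap in the analysis plan. The exposure is undefined, and no study-day or within/between-person term is named anywhere. The coefficient as stated can therefore mix a use effect with time trend and between-person differences, and its sign can depend on the coding. The direction of these biases follows from simple arithmetic. Their size is illustrative: with no drift and no confounding, the codings in the main simulation rejected in roughly 4% to 7% of runs.

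The *impact* wording is a separate matter. It fails on the design reasons above, and also because Aim 2's exposure (reductions in cognitions and bias, measured only at the three assessments) is not the modelled exposure (app use).

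**What to change.** In Data Analysis and Statistical Considerations:

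1. Fix one exposure definition before analysis. An example is a session completed (yes/no) on each study day, taken from the time stamps and counting only sessions completed before the diary. Given the 57% above, add a daytime/nightly indicator or use the nightly diary for the main result. No single window is clearly best; what matters is choosing it in advance.
2. Include study day, the person's mean use, the deviation from that mean, a random intercept and serially correlated residuals. With 14 people, treat the person-mean coefficient as descriptive.
3. State whether periods are fitted separately or as one model per outcome with a period interaction. Either is acceptable; the second matches the stated three models.
4. Report the within-person coefficient with its 95% interval as an exploratory association. Add a sensitivity analysis with lagged use (session on the previous study day) for distress-driven skipping. It will miss an effect lasting under a day, and its error rate with serially correlated residuals has not been checked here.
5. Replace *impact* with *association* wherever Aim 2 or its EMA analysis is described: Purpose, Background and Significance, Aims and Design.

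The cost is a few lines of text and SAS code, with no new data if time stamps are kept; confirm this for the first two cohorts as well as the Qualtrics cohort.

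Two limitations should be stated. Study day absorbs any benefit that builds up over sessions: in the second simulation, cumulative sessions and study day correlated about 0.99 within person, so these data cannot separate the two. Reverse causation also remains possible.
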